#### **4.6 Protocol Deviations and Blind Data Review Meeting**

Protocol Deviations and Non-Compliances will be handled and reviewed regularly during the study according to a study specific 'Protocol Deviation and Non-compliance Management Plan' created in line with Syneos Health controlled document 'Processing and Management of Protocol Deviations (3101.W02)'. All Protocol Deviations and Non-Compliances will be consolidated into one workbook outside of the eCRF for regular review of each entry in terms of its classification of Minor or Major and any effect on efficacy.

	Plus-Project Statistical Analysis Plan	
	Protocol Number: GALACTIC-1	Version: 1

Shortly prior to database lock and unblinding of subject’s treatment assignment, a BDRM will take place to adjudicate SAP definitions, protocol deviations and any other non-compliances, and agree on exclusions from the PP Set. Additionally, any further actions related to the database, SAP and/or Protocol Deviations and Non-Compliances workbook may be discussed and actioned. Decisions and actions agreed at the BDRM (including any follow-up notes) will be documented.

The strategy for the presentation of results by the ‘treatment received group’ will be discussed and agreed at the BDRM.

## **5. GENERAL METHODS AND PRINCIPLES**

The SAP will be finalized and signed-off prior to DBL and unblinding. Any post-hoc analysis (analyses performed post DBL that are different from those described in the final version of the SAP) will be documented in the final clinical study report (CSR) as changes to the planned analysis.

All data collected will be listed, sorted by strata/treatment group, Subject ID, visit and time, with the Primary Population listed first as follows:-

- SoC2/Monotherapy Placebo,
- SoC2/Monotherapy GB0139 3 mg,
- SoC2/Monotherapy GB0139 10mg,
- SoC1/Combination Placebo,
- SoC1/Combination GB0139 3 mg,
- SoC1/Combination GB0139 10mg,
- Screening Failures.

Data on screening failures will be listed only.

Tabulations and data analyses will be performed using SAS® software, version 9.4 or later (SAS Institute, Inc.).

Unless otherwise specified, efficacy analyses will be performed in the mITT Analysis Set, with sensitivity analyses of the primary endpoints and secondary endpoints conducted using the PPS. Safety summaries will be performed using the SS Analysis Set. The ITT Analysis Set will be used to describe demographics, baseline characteristics and medical history.

The populations will be split according to SOC1 / Monotherapy and SOC2 / Combination, as well as per treatment group.

	Plus-Project Statistical Analysis Plan	
	Protocol Number: GALACTIC-1	Version: 1

P-values will be generated for all efficacy treatment comparisons, in all populations, as an exploratory tool for detection of potential contrasts in the material. P-values will not be generated for subgroup analyses.

## 5.1 Standard Descriptive Statistics

### *Continuous variables*

Unless specified otherwise, the following standard descriptive statistics by treatment group will be obtained for continuous variables: number of subjects with non-missing values, mean, standard deviation, median, 25th percentile, 75th percentile, minimum and maximum value.

### *Categorical variables*

Unless specified otherwise, the following standard descriptive statistics by treatment group will be presented for categorical values: total number, number of values in each category and the corresponding percentage of the total number of non-missing values will be calculated.

## 5.2 Definition of Analysis Visits

Assessments will be mapped to analysis visits for a variable as follows:

- Find the closest non-missing, within time-window (as per Table 1 below) result taken to the scheduled day as per the protocol schedule of assessments.
- If two assessments are equal distance either side of the scheduled day, then take the earlier result.

	Plus-Project Statistical Analysis Plan	
	Protocol Number: GALACTIC-1	Version: 1

**Table 1: Study visits and analysis visit windows**

Visit	Description	Scheduled Day	Analysis window, Primary Population	Analysis window, SoC1 / Combination and SoC2 / Monotherapy Populations	Analysis Visit
V2	Baseline / Randomization	1	n/a	n/a	Baseline
V3	Visit 3 / Week 4	29	2-43	2-43	Week 4
V4	Visit 4 / Week 8	57	44-71	44-71	Week 8
V5	Visit 5 / Week 12	85	72-134	72-134	Week 12
V6	Visit 6 / Week 26	183	135-232	135-232	Week 26
V7	Visit 7 / Week 40	281	233-323	233-323	Week 40
V8 [a]	Visit 8 / Week 52	365	324-453	324-453	Week 52
V8 [b]	Visit 8 / Week 52	365	>=324	324-453	Week 52
FUV1 [a]	Follow-up 1 / Week 76	541	454-635	454-635	Week 76
FUV2 [a]	Follow-up 2 / Week 104	728	>=636	>=636	Week 104

[a] Subjects recruited under original design only.

[b] Subjects recruited under the updated design only.

Note: For the updated design, at the Follow up visit 7 days after the final study day visit only adverse events and concomitant medications are collected (does not require analysis visit windows).

All efficacy data will be considered for efficacy summary tables (i.e. summary tables by visit will include Week 76 and Week 104) but all data post Day 453 will be omitted from the efficacy analysis tables and any efficacy figures presented by visit will only be up to Week 52.

For time to event endpoints, Day 379 (Week 52 plus 2 weeks) will be considered the end of the period under consideration.

All safety data collected will be included in summaries.

In the proceeding sections of this SAP visit will mean analysis visit assignment per Table 1 unless stated otherwise.

	Plus-Project Statistical Analysis Plan	
	Protocol Number: GALACTIC-1	Version: 1

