14.5.2 Safety Analysis

The primary assessment of benefit-risk of GB0139 3 mg compared to Plc will be based on efficacy and safety data over 52 weeks. All safety assessments described below will focus on

data collected within the first 52 weeks of the study. In addition, selected safety analyses will be repeated to include data collected beyond 52 weeks; further details will be specified in the SAP.

All treated subjects will be included in the safety analysis. The primary safety assessment will be based on the participants who received 3mg or placebo as study treatments. A separate safety assessment will be made for the participants who received study treatment in combination of nintedanib or pirfenadone. The particular tables and figures to be split in this way will be specified in the SAP. In general, safety analyses will be descriptive in nature. No hypothesis testing is planned.

Kaplan-Meier plots will be produced for the time to premature treatment discontinuation. Statistical analysis and reporting of adverse events will concentrate on treatment-emergent adverse events. All adverse events occurring between start of treatment and end of the residual effect period will be considered 'treatment-emergent'. The residual effect period is defined as the 28 days after the date of the last dose of trial medication. Adverse events that start before first drug intake and deteriorate under treatment will also be considered 'treatment-emergent'. Frequency, severity, and causal relationship of adverse events will be tabulated by system organ class and preferred term after coding according to the current version of MedDRA.

Laboratory data will be analysed both quantitatively as well as qualitatively. The latter will be done via comparison of laboratory data to their reference ranges. Values outside the reference range as well as values defined as clinically relevant will be highlighted in the listings. Treatment groups will be compared descriptively with regard to distribution parameters as well as with regard to frequency and percentage of subjects with abnormal values or clinically relevant abnormal values.

Vital signs, physical examinations, or other safety-relevant data observed at screening, baseline, during the course of the treatment and at the end-of-treatment evaluation will be assessed with regard to possible changes compared to findings before start of treatment.

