### 1.1 Trial design

A randomized, double-blind, multicentre, parallel, placebo-controlled phase 2b study in subjects with idiopathic pulmonary fibrosis (IPF). All subjects enrolled into the study should have a diagnosis of IPF established within the previous five years, and a diagnostic HRCT scan assessed by central independent radiologists according to the ATS/ERS/Fleischner criteria available within the previous 12 months prior to screening.

The original design consisted of 3 treatment groups, placebo, GB0139 3mg and GB0139 10mg, with patients randomized in a 1:1:1 ratio. Stratification in the original version of the study was according to the patient's standard of care treatment at enrollment;

- SoC1 being patients currently treated with either pirfenidone or nintedanib,
- SoC2 being patients not currently treated with pirfenidone or nintedanib.

A subject's SoC must have been deemed as stable by the Principal Investigator or treating physician before their enrollment in the study.

It was initially planned to randomize approximately 450 patients to this design across approximately 70 sites from the European Union and 30 sites from the United States. This design was intended to evaluate the efficacy and safety of GB0139 over 52 weeks of dosing in addition to the subject's current standard of care (SoC) (including treatment with either pirfenidone or nintedanib). It was planned to continue blinded treatment beyond week 52 and up to week 104 to provide further safety follow-up information.

Following a review of unblinded efficacy and safety data by the study's DSMB in February 2021, the study design has been modified based on the DSMB's recommendation. Participants randomized to the 10mg GB0139 group, and all those taking nintedanib or pirfenidone, have been discontinued from the study. In addition, subjects who had already

	Plus-Project Statistical Analysis Plan	
	Protocol Number: GALACTIC-1	Version: 1

completed 52 weeks of treatment were discontinued. In total, about 320 subjects had been randomized under the original design, and approximately 200 were discontinued.

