##### **7.2.4.3 Change from baseline in diffusion capacity of the lung for carbon monoxide (DLCO), corrected for HB, at 52 weeks**

Data from an external vendor with the DLCO result (mmol/min/kPa) will be used. The same analyses (ANCOVA) as detailed in Section 7.2.4.2 will be used but using the baseline DLCO rather than baseline 6MWT in the ANCOVA model.

Data collected at early withdrawal visit will be summarized descriptively only.

	Plus-Project Statistical Analysis Plan	
	Protocol Number: GALACTIC-1	Version: 1

7.2.4.4 Change from baseline at week 52 in dyspnea assessment by University of California San Diego - Shortness of Breath Questionnaire (UCSD - SOBQ)

Data from an external vendor with the UCSD – SOBQ scores will be used. The UCSD – SOBQ comprises of 24 items scored 0-5 where (0 = "not at all" to 5 = "maximal or unable to do because of breathlessness"). The item scores will be summed (treating any missing as 5) to derive a total score between 0 and 120. The UCSD – SOBQ items are provided in Section 11.7. The same MMRM analysis as detailed in Section 7.2.3.2 will be used for the change from baseline at week 52 in UCSD – SOBQ Total Score, using the baseline UCSD – SOBQ Total Score rather than the baseline SGRQ Total Score.

7.2.4.5 Change from baseline at Week 52 for HRQoL as assessed by Short Form Survey (SF-36)

Data from an external vendor with the SF-36 scores will be used. The change from baseline in SF-36 total score will be analyzed using an MMRM the same as detailed in Section 7.2.3.2 using the corresponding baseline SF-36 total score rather than the baseline SGRQ total score.

In addition, the actual and change from baseline in individual component scores as follows will be summarized by treatment group and visit:

- Physical component scale (PCS) and mental component scale (MCS).
- Physical functioning (PF), role physical (RF), bodily pain (BP), general health (GH), vitality (VT), social functioning (SF), role emotional (RE) and mental health (MH).

The details of scoring are provided in Section 11.8.

7.2.4.6 Percentage of subjects with Adverse Events (AE) or Serious Adverse Events (SAE) over 52 weeks

Only TEAEs with a start date prior to Day 379 will be considered for inclusion in the analysis. Summaries of the percentage of subjects with AE or SAEs will be presented for each population by SOC and PT. No formal analyses will be performed.

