- All deaths (Note: time to death is limited to a follow-up period of Day 379)

	Plus-Project Statistical Analysis Plan	
	Protocol Number: GALACTIC-1	Version: 1

Further summaries by SOC and PT will be produced for all TEAEs, TEAEs by SoC, PT and maximum severity, treatment related TEAEs, serious TEAEs, TEAEs leading to treatment discontinuation and TEAEs leading to death. These will be presented by SOC and PT, sorted by decreasing frequency overall and then alphabetically. An additional summary all AEs post follow-up (i.e. post treatment end date + 14) will be produced by SOC and PT.

Additional summaries of all TEAEs and of serious TEAEs by PT only, sorted by decreasing frequency overall, will be presented.

Summaries of COVID related (per eCRF) TEAEs and serious COVID related TEAEs will also be produced. In addition, summaries of TEAEs and Serious TEAEs related to IPF exacerbations (i.e. those events marked on the eCRF as related to IPF exacerbation) will be provided.

Serious TEAEs and TEAEs leading to discontinuation of study drug will be presented separately for the SoC1 / Combination and SoC2 / Monotherapy Populations.

Additionally, the incidence of by time period (0 - 13 weeks, >13 weeks – 26 weeks, >26 weeks - 39 weeks, >39 weeks – 52 weeks, ≥ 52 weeks) will be presented. The presentation will include all TEAEs, serious TEAEs, TEAEs leading to treatment discontinuation, and TEAEs leading to death. The denominator for each period will be the number of subjects on treatment at the beginning of that time period. This summary will be repeated for the SoC1 / Combination and SoC2 / Monotherapy Populations.

Each TEAE event rate (per 100 patient years) will also be summarised by preferred term within each system organ class. For each preferred term, the event rate will be presented and will be defined as the number of patients with that AE divided by the sum of the duration from the start of treatment to 14 days after the last treatment dose (for patients without the event) and the time to the AE (for patients with the event) in each group multiplied by 100. This will also be repeated for serious TEAEs.

Risk differences for proportion of subjects with the following TEAEs (with associated 95% confidence intervals) comparing GB0139 groups to Placebo will be estimated:-

- TEAE
- TEAE by maximum severity (overall and within related TEAEs)
- TEAE by maximum relationship to study drug (overall and within serious TEAEs)
- Serious TEAE

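### SAP 5.2 and 7.3.2 drop the protocol's 52-week basis for adverse-event incidences and risk differences without declaring it, so in the pooled population these outputs compare unequal follow-up per patient

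*SAP*

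**What the plan says.** **Protocol.** Section 14.5.2 directs the safety assessments to "data collected within the first 52 weeks of the study" and adds that "selected safety analyses will be repeated to include data collected beyond 52 weeks", with details left to the SAP.

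**SAP, general rule.** The notes under Table 1 in SAP 5.2 say "All safety data collected will be included in summaries". SAP 7.3.2 then plans crude incidences of TEAEs, serious TEAEs, and TEAEs leading to discontinuation or death. It also plans "Risk differences for proportion of subjects with the following TEAEs", with 95% confidence intervals. Neither carries a 52-week limit. Section 9, which lists departures from the protocol, is silent on this.

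**SAP, outputs that are limited.** For the secondary endpoint in 7.2.4.6, "Only TEAEs with a start date prior to Day 379 will be considered for inclusion in the analysis". SAP 5.2 ends all time-to-event endpoints at Day 379. Time to premature treatment discontinuation (7.3.8) counts only discontinuations before Day 358.

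**Who could be followed longer.** SAP 1.1 says of the original design: "It was planned to continue blinded treatment beyond week 52 and up to week 104 to provide further safety follow-up information". That design was allocated 1:1:1, hence 1:1 between 3 mg and placebo. Under the updated design allocation is 2:1 and treatment lasts 52 weeks. SAP 1.3 pools both cohorts in the Primary Population.

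**The concern.** The SAP makes all collected data the basis of the 7.3.2 tables, where the protocol makes the first 52 weeks the basis and later data an addition. This is more than loose drafting. SAP Table 1 gives the Primary Population Week 76 and Week 104 windows for original-design subjects, and both the exposure summary (7.3.1) and the period table (7.3.2) have a category for time beyond 52 weeks.

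The extra time is not shared evenly. It can arise only in the 1:1 cohort, and that cohort is a larger part of the placebo arm than of the 3 mg arm. A crude proportion rises with time observed, so an uncut risk difference mixes any drug effect with a difference in follow-up. The redesign followed a review by the data monitoring board of unblinded efficacy and safety data, so this comparison will be read closely. The same event may also appear with one percentage in 7.2.4.6 and another in 7.3.2.

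**Working it through.** **Plan's own figure.** The documents state no figure for this imbalance. The total of 141 used below does agree with the sample-size statement: 47 placebo and 94 on 3 mg give 100 / (240 × √(1/47 + 1/94)) = 2.33; 2.33 − 1.645 = 0.69; power 75.4%, against the stated 75%.

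**Inputs from the documents.** Allocation 1:1 (original) and 2:1 (updated); treatment planned to Week 104 (original) and to Week 52 (updated); 141 subjects.

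**Assumed inputs.** The documents do not give these:
- m: original-design subjects in the Primary Population, 30 to 120
- f: fraction of them with time beyond Week 52, 0.25 to 1, the same in both arms
- e: extra years for that fraction, 0.5 to 1
- R: 52-week risk of the event, 10% to 60%, with the same constant hazard in both arms

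**Formula.** With no drug effect, each arm's crude proportion is R + f × s × [(1 − R) − (1 − R)^(1+e)], where s is the original-design share of that arm. The spurious difference (3 mg minus placebo) is therefore −f × (s_placebo − s_3mg) × [(1 − R) − (1 − R)^(1+e)].

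**Example: m = 60 of 141, f = 0.5, e = 0.5, R = 30%.**
- Original subjects split 30:30; the 81 new subjects split 27 placebo and 54 on 3 mg. Arms: 57 and 84.
- Shares: 30/57 = 52.6% on placebo, 30/84 = 35.7% on 3 mg.
- Total extra time: 30 × 0.5 × 0.5 = 7.5 patient-years in each arm. Mean possible follow-up: 1 + 7.5/57 = 1.13 years on placebo, 1 + 7.5/84 = 1.09 years on 3 mg.
- Bracket: 0.70 − 0.70^1.5 = 0.114.
- Crude proportions: 33.0% placebo, 32.0% on 3 mg. Difference −1.0 point.

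**Range.**

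| Case | Difference, 3 mg minus placebo |
|---|---|
| m = 120, f = 0.25, e = 0.5, R = 10% | −0.1 point |
| m = 60, f = 0.5, e = 0.5, R = 30% | −1.0 point |
| m = 60, f = 0.5, e = 1, R = 30% | −1.8 points |
| m = 60, f = 1, e = 1, R = 60% | −4.1 points |
| Extreme: every original subject followed to Week 104 (m = 68, R = 50%) | −4.3 points |

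The protocol gives about 141 as the trial total, while SAP 1.1 can be read as 141 new subjects in addition to the original ones. On that second reading the cases computed gave −0.2 to −4.1 points.

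**Dependence on equal persistence.** In the example the sign reverses if the fraction continuing past Week 52 on 3 mg exceeds 84/57 = 1.47 times that on placebo.

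**Patient-year rates (m = 60, f = 0.5, e = 0.5, hazard 0.35 in year 1).**

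| Hazard after year 1 | Placebo | 3 mg |
|---|---|---|
| unchanged | 35.0 | 35.0 |
| halved | 33.3 | 33.8 |
| 1.5-fold | 36.5 | 36.1 |

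The rates remove the artefact when the hazard is constant and can lean slightly either way when it is not.

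**After a common cut.** With the extra time removed, the artefact in crude proportions is 0 in this model.

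**The case against.** The case on the other side is substantial.

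- **Much is already limited to about 52 weeks.** The protocol's named adverse-event endpoint is cut in 7.2.4.6, by system organ class and preferred term and for each population. Death and hospitalization end at Day 379 as time-to-event endpoints, and premature discontinuation is limited to before Day 358. This stands, and it confines the point to the 7.3.2 incidences and risk differences.
- **Unequal follow-up is partly handled.** The period table covers all TEAEs, serious TEAEs, and TEAEs leading to discontinuation or death, and takes as denominator those still on treatment when each period opens. In addition, "Each TEAE event rate (per 100 patient years) will also be summarised by preferred term within each system organ class", repeated for serious TEAEs. This stands in part: neither output corrects the risk differences, which are the between-arm safety contrasts that carry confidence intervals.
- **The effect is small against the noise.** With arms of 57 and 84 and 30% incidence, the 95% half-width is 1.96 × √(0.21 × (1/57 + 1/84)) = 15.4 points. The protocol treats the safety analyses as descriptive, without tests. Subjects past Week 52 were discontinued at the redesign, which limits the extra time. All this stands and argues for a modest rating.
- **The direction is conditional.** TEAEs count only to 14 days after the last dose, so different persistence between arms could shrink or reverse the lean. This stands.
- **Late events matter.** Removing them from every between-arm table would go further than the protocol, which keeps an all-data repeat. This stands and shapes the fix.
- **Version.** The SAP was written against protocol version 7.0; the supplied protocol refers to 6.1_UK. That 14.5.2 is the same in both is an assumption.

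**Conclusion.** The conflict between protocol and SAP on the safety period can be read directly from the text and is not declared in Section 9. It affects the crude TEAE, serious TEAE, discontinuation and death incidences in 7.3.2, and the risk differences with their 95% intervals. In those outputs the comparison leans modestly towards 3 mg, by about 0 to 4 points, if hazards and persistence past Week 52 are equal in the two arms. The size rests wholly on assumed inputs, because the number of original-design placebo and 3 mg subjects in this population who passed Week 52, and for how long, is not given.

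A reader might infer that the safety results as a whole are tilted to make 3 mg look safer, or that placebo collects more extra time in total. The documents support neither. Original-design allocation was 1:1, so with equal persistence total extra time is the same in both arms and only time per patient differs. Several safety outputs are already cut or use suitable denominators, and the patient-year rates can lean either way. The point is worth correcting before database lock, but it is a limited one.

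**What to change.** In SAP 5.2 and 7.3.2, make the primary presentation of the TEAE incidence tables and the risk differences cut at the Day 379 limit already used in 7.2.4.6. Keep all-data versions of selected tables, including late serious and fatal events, as the supplementary repeat that Protocol 14.5.2 describes. If the team prefers all data as the basis, Section 9 should say so and give the reason. Stratifying the risk differences by design cohort is optional.

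The cost is a change of SAP wording and a date filter that the SAP already applies elsewhere. The downside is that late events appear only in the supplementary tables, so those tables should be cross-referenced from the primary ones.

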6.2 Number of Participants

Approximately 141 participants in total will be randomized in GALACTIC-1.

Participants are considered evaluable if they have taken at least one dose of the double-blind treatment.

Participants who prematurely discontinue double-blind study treatment after randomization can remain in the study and complete the remaining scheduled visits, if possible.

Any participants who withdrawn from the study after randomization cannot be replaced and re-screened.

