10.5 Discontinuation of study treatment

Temporary discontinuation of GB0139 for <2 weeks will be permitted, if for reasons other than those stated below. The reason for discontinuation should be documented in the eCRF.

Treatment with study drug may be permanently discontinued for any of the following reasons:

- Persistent non-adherence by subject
- Adverse event assigned to the investigational drug
- Overall unsatisfactory therapeutic response
- Study terminated by sponsor
- Withdrawal by subject
- Lost to follow-up
- Other (cause to be elaborated on in the subject's file)

In all cases, participants should be encouraged to discuss any potential study treatment discontinuation with the investigator prior to stopping treatment. If considered medically appropriate by the PI, participants who have been withdrawn from study treatment can remain in the study, resume their usual standard of care treatment for IPF, if applicable, and complete scheduled visits and study assessments up to the follow up phone call.

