### 7.3.4 Laboratory Data

Système International (SI) units provided by a central laboratory will be used for presenting all laboratory values.

Values below the lower limit of quantification (LLOQ) will be replaced by the value of the LLOQ.

The hematology and clinical chemistry parameters to be summarized are as follows:

- Hematology: Hematocrit, Hemoglobin, Leukocytes with differential count, Platelet (count)
- Clinical chemistry: Albumin, Alkaline phosphatase (ALP), Aspartate aminotransferase (AST), Alanine aminotransferase (ALT), Bilirubin (total), Calcium, Creatinine, Glucose, Potassium, Sodium

The values provided by the central laboratory in standard units as well as the flags for Low/Normal/High (L/N/H) values relative to the normal range or Normal/Abnormal classifications will be used for summaries.

	Plus-Project Statistical Analysis Plan	
	Protocol Number: GALACTIC-1	Version: 1

For the continuous parameters, the results and the change from baseline (for post baseline assessments) will be summarized by treatment and visit. This summary will be repeated in the SoC1 / Combination and SoC2 / Monotherapy Populations.

For any categorical parameters (including incidence of abnormalities), the results will be summarized by treatment and visit based on the number of subjects with non-missing data at the visit as the denominator.

Separate subject listings of abnormalities across all populations, sorted by SoC, will be presented showing all data within the abnormal parameter over the study for the respective subject.

All laboratory results will be listed, including all unscheduled visits.

Serum pregnancy results (at screening) and urinary pregnancy results (post-screening) will be listed per subject and visit.

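### By-visit laboratory, ECG, vital-sign and physical-examination tables combine readings on study drug with readings taken after it was stopped, and do not show how many of each there are

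*SAP*

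**What the plan says.** **Visit assignment.** SAP 5.2 gives the mapping rule: "Find the closest non-missing, within time-window (as per Table 1 below) result taken to the scheduled day". Table 1 sets the windows in study days. The notes below it add "All safety data collected will be included in summaries" and then fix the meaning of the word visit for the rest of the plan: "In the proceeding sections of this SAP visit will mean analysis visit assignment per Table 1 unless stated otherwise". Drug status is not a criterion anywhere in the rule.

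**Safety tables.** For laboratory data, SAP 7.3.4 says "For the continuous parameters, the results and the change from baseline (for post baseline assessments) will be summarized by treatment and visit". Sections 7.3.5 (vital signs), 7.3.6 (ECG) and 7.3.7 (physical examination) are built the same way. SAP 7.3 uses the Safety Set, which selects subjects with at least one dose; it does not select on-drug records.

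**Attendance after stopping.** Under Protocol 6.2, participants who stop study treatment early "can remain in the study and complete the remaining scheduled visits, if possible". Protocol 10.5 adds that, where the investigator considers it medically appropriate, "participants who have been withdrawn from study treatment can remain in the study, resume their usual standard of care treatment for IPF, if applicable".

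**Protocol analysis text.** Protocol 14.5.2 says that vital signs, physical examinations and other safety-relevant data seen at screening, baseline, "during the course of the treatment and at the end-of-treatment evaluation will be assessed with regard to possible changes" from the pre-treatment findings. It gives no rule for handling readings taken after the last dose.

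**The concern.** A by-visit safety table is normally read as showing what happens to people taking the drug for that long. Here the Week 26, 40 and 52 columns for GB0139 3 mg can include people who stopped months earlier. If a laboratory or ECG change fades once the drug is withdrawn, their values pull the arm mean or abnormality rate back towards where it would be without drug.

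Under Protocol 8.3.1, participants may take nintedanib or pirfenidone only after withdrawing from study treatment. Off-drug readings may therefore carry the effects of another therapy, and Protocol 4.1 describes potentially significant adverse effects with both.

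The tables as planned give the reader no count of off-drug readings. Neither dilution nor contamination could be judged from them. The later visits are the ones that inform longer-term safety and the ones where off-drug readings accumulate.

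**Working it through.** The documents state no figure on this point, so there is none to reproduce. The check is a reading of the rules, followed by an illustration with assumed inputs.

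**1. Do off-drug readings reach the tables?** Protocol Table 1 schedules laboratory tests, vital signs and physical examination at every visit to Week 52, and ECG at every visit except Week 40. Take a subject who stops on Day 90 and keeps attending. Scheduled days are from SAP Table 1.

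| Visit | Scheduled day | Days since stopping |
|---|---|---|
| Week 26 | 183 | 183 − 90 = 93 |
| Week 40 (no ECG) | 281 | 281 − 90 = 191 |
| Week 52 | 365 | 365 − 90 = 275 |

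All three fall outside every post-dose limit in the documents: 14 days (SAP 7.3.2, main definition), 30 days (SAP 7.3.2, partial dates) and 28 days (Protocol 14.5.2, residual effect period). All three are tabulated under the treatment arm. The only half-life given is about 6 hours, from animal studies (Protocol 8.6). Two days is 48/6 = 8 half-lives, leaving 0.5^8 ≈ 0.4% of the drug. That describes exposure, not how long an effect lasts.

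**2. Does the SAP use drug status elsewhere?** It does:

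| Output | Use of drug status |
|---|---|
| Treatment-emergent adverse events (7.3.2) | Up to last dose + 14 days |
| Adverse events by time period (7.3.2) | Denominator is subjects on treatment at the start of the period |
| COVID-19 (7.3.9) | Split into on treatment and post treatment |
| FVC Supplementary Analysis 1 (7.2.2.3) | Excludes values after stopping |
| Laboratory, vital signs, ECG, physical examination (7.3.4 to 7.3.7) | None |

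**3. How large could the dilution be?** Let f be the share of GB0139 readings at a visit taken off drug, and r the share of the effect that reverses. Both are assumed. A share 1 − f shows the full on-drug difference D, and a share f shows (1 − r)D. The tabulated difference is

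(1 − f)D + f(1 − r)D = D(1 − f × r).

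| f | r = 1 | r = 0.5 | r = 0 |
|---|---|---|---|
| 5% | 95% | 97.5% | 100% |
| 10% | 90% | 95% | 100% |
| 20% | 80% | 90% | 100% |
| 30% | 70% | 85% | 100% |
| 40% | 60% | 80% | 100% |

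The entries are the percentage of D that remains in the table. For an abnormality rate, suppose 10% on drug against a 4% background, with full reversal:

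- f = 20%: 0.8 × 10% + 0.2 × 4% = 8.8%
- f = 30%: 0.7 × 10% + 0.3 × 4% = 8.2%

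The formula assumes that off-drug subjects otherwise resemble on-drug subjects and have not started another IPF drug. If they have, the direction of the distortion is no longer fixed.

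**The case against.** The strongest reply is that this is a stated choice. The SAP says openly that all safety data collected enter the summaries, and tabulating everything collected from treated subjects is a legitimate descriptive convention. That stands, and it is why the all-data tables should stay. It does not explain why these tables alone lack the on/off split used for other outputs.

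A reader might infer that the SAP departs from Protocol 14.5.2 and should have declared this in its Section 9. The documents do not support that. The quoted protocol wording concerns vital signs, physical examinations and other safety-relevant data; the laboratory paragraph before it has no on-treatment wording. The phrase about the course of the treatment can be read as the 52-week treatment period. Protocol 14.5.2 frames the safety assessments by the first 52 weeks of the study, and its residual effect period is tied to adverse events.

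A reader might also infer that a subject who stops because of an abnormal test disappears from view. That is not so. Protocol 11.1.3 allows a laboratory value that leads to discontinuation to be assessed as an adverse event, and Protocol 11.2 treats clinically relevant deterioration as one. SAP 7.3.2 tabulates events leading to treatment discontinuation by term and by period, and as a risk difference. SAP 7.3.4 lists every laboratory result, and SAP 7.3.8 plots time to discontinuation. These outputs protect individual cases. They do not correct arm-level means or abnormality rates.

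The share that matters is also smaller than the share who stop, because only those who keep attending contribute. Protocol 10.6 ends data collection at study withdrawal, and the roughly 200 subjects discontinued at the redesign left the study (SAP 1.1).

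**Conclusion.** The gap is real and modest. The by-visit tables in SAP 7.3.4 to 7.3.7 mix on-drug and off-drug readings across subjects within an arm, and nothing in either document separates them.

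It would go too far to say that every drug effect is pulled towards placebo. Only effects that reverse are diluted, lasting effects are not, and values taken on nintedanib or pirfenidone may move either way. The size cannot be computed, because neither document gives a discontinuation rate or an off-drug share. The figure of 80% (or 90%) of the difference remaining rests on an assumed 20% off drug with full (or half) reversal.

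No hypothesis test is affected, since Protocol 14.5.2 makes the safety analyses descriptive. This is an inexpensive improvement to how the tables can be read; it does not show the planned tables to be invalid.

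**What to change.** In SAP 7.3, keep the all-data by-visit summaries and add two sets of rows, each with its n, for laboratory, ECG, vital-sign and physical-examination data:

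- **On treatment:** readings from first dose to last dose plus the post-dose window finally adopted for treatment-emergent adverse events.
- **Post treatment:** readings after that window.

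The 14, 28 and 30 days in the documents must first be reconciled, so that one window serves both the adverse-event tables and these.

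No new data are needed. SAP 7.3.1 and 7.3.2 already draw the date of last dose from the eCRF, so the work is one date flag and a few extra rows. The on-treatment rows will be smaller at late visits and will describe the subjects who stayed on drug, which can itself make late values look benign. They should be read beside the discontinuation data. For the same reason they should not replace the all-data tables.
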